## 5. Participant Enrollment

Participants will be identified and recruited from outpatient clinics. Participants will be presented with a study consent form. The point of enrollment is after the patient has met the inclusion/exclusion criteria, and has signed the study consent form. Run-in Participants (the first 1 to 4 recruited) are to be consented using the Run-in consent form. Run-in Participants follow the same assignment as described in Group 1 but are NOT randomized. After the Run-in phase, subsequent Participants are consented using the Randomized Consent Form and then randomized to Group 1, Group 2, or Group 3. This is further detailed in the section on "Screening and Informed Consent."

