## **8.2 Run-in Participants, Randomization to Treatment Groups, and Treatment Rules**

All sites will be allowed to enroll between one and four Run-in Participants. Run-in Participants are necessary for the study staff to demonstrate adequate knowledge and training using the Ekso device and to practice the data collection process that is required for this study. Run-in Participants are *not* randomized; they will be enrolled using a separate consent form. Run-in participants will train in the Ekso device for 12 weeks (36 sessions) and assessments will be done according to the Group 1 schedule except run-in participants will not complete the follow up evaluation visit and assessments (week 24). It is not required for a site to complete all 12 weeks of training with all Run-in Participants before beginning the screening, enrollment, randomization, and baseline tests of other Participants. All subsequent study Participants are randomized via computer to one of three treatment arms, either Group 1, 2 or 3 defined respectively as Ekso intervention, active control or passive control in a 2:2:1 randomization ratio (respectively). Group 1, 2, or 3 descriptions are as follows:

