If the participant continues to meet criteria for this study the following data will be collected as *baseline data*. **NOTE: All Participant evaluations are conducted outside of Ekso, BWSTT, or BWS for overground walking. Baseline examinations may not occur more than 30 days prior to initiation of the training regimen:**

1. 10 Meter Walk Test (10MWT), at both self-selected and fast speeds
2. GAITRite Pressure Map for Temporospatial Gait Parameters (if site has one)
3. Timed Up and Go (TUG)
4. 6 Minute Walk Test (6MWT)
5. Spinal Cord Injury Functional Ambulation Inventory (SCI-FAI)
6. Walking Index for Spinal Cord Injury (WISCI II)
7. Upper and Lower Extremity Muscle Strength
8. Berg Balance Scale
9. The Spinal Cord Assessment Tool for Spastic Reflexes (SCATS)
10. Spinal Cord Independence Measure III (SCIM-III), Mobility subscale only, by interview
11. Modified Ashworth Scale
12. Spinal Cord Injury Spasticity Evaluation Tool (SCI-SET)

13. Numeric Rating Scale for spasticity
14. International SCI Quality of Life Basic Data Set
15. Epidemiological Studies Depression Scale (CES-D 10)
16. Borg Scale for maximal Rate of Perceived Exertion (collected at baseline 6MWT and at training session 1)
17. International SCI Pain Basic Data Set
18. Modified International SCI Bowel Function Basic Data Set
19. Modified International SCI Lower Urinary Tract Basic Data Set

See Appendix A for description of assessments.

The following data will be collected *per session*:

1. Any adverse events/complications (related to Participant or staff) noted following prior training session and during present session
2. Assessment of skin integrity of the anterior and posterior torso, anterior tibia, sacral area and bilateral feet (before and after training)
3. Walk time\*
4. Stand time\*
5. Seated rest time
6. Number of steps total and in each mode\* or number of steps at each BWS%
7. Time spent in each mode\* or time spent at each BWS%
8. Any equipment used for training, including type of assistive device and braces
9. Number of therapists/staff required at each training session to ensure the safety of the Participant and to complete the training session goals
10. Amount of assistance (e.g. min, mod, max) as reported by staff members at each training position (hips, trunk, right LE, left LE, etc.)

\* For Group 1 Participants, these data are *automatically collected* by Ekso (in Ekso Pulse) at the end of each training session

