**Footnotes (Table 2):**

† Height may be obtained verbally; weight must be measured via scale. Calculate BMI using NIH National Heart Lung and Blood Institute calculator at: [http://www.nhlbi.nih.gov/health/educational/lose\\_wt/BMI/bmicalc.htm](http://www.nhlbi.nih.gov/health/educational/lose_wt/BMI/bmicalc.htm)

\* Skin assessment to be performed before and after training sessions

• Maximum Borg to be done during session 1 then during weekly sessions (every third session) thereafter, and after 6 minute walk test during evaluations

\*\* Assessments to be performed outside of exoskeleton or any body weight support and on a non-training day.

◦ Vital signs (BP and HR) will be measured as follows:

- °° Upon relaxation (5 minutes) in sitting position after arrival. After 1 minute of standing (may hold on to something for balance or use standing in frame as needed)
- °°° Vitals should be taken in sitting before and immediately after 6 minute walk
- ↳ To be taken prior to 10MWT
- " To be taken prior to each session and needed only if orthostatic hypotension was present at the time of the previous session and/or if symptomatic upon standing at the time of the current session.

♦ Run In will follow Group 1 assessments but will not complete the follow up evaluation visit and assessments

^ To be obtained during Screening, and if participant passes screening can be used for Baseline

† Numeric Pain Scale: to be completed before and during session 1 and weekly thereafter

¤ To be done by blinded evaluator for comparison to week 6, 12, 24 (midpoint, endpoint, and follow-up) evaluation visit results.

☆ Done by blinded evaluator for comparison. Testing to be done according to ISNCSCI instructions (supine, using the correct limb positioning and angles for resistance)

 May occur over one or two visits

 B = before session, D = during session, A = after session

 Passive Group 3 will complete all evaluations at Baseline, Week 6 and week 12, the same as Groups 1 and 2, then have the option (per participant decision) to undergo 12 weeks of training using the exoskeleton or standard gait training. The optional 12 week period will consist of training only. No further evaluations will be completed at this time.

Update Concomitant Medication Log accordingly

To include shoulder flexion/extension, abduction/, and triceps

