Adverse events (AE) data collection must begin once the Participant has signed the informed consent document. AEs will continue to be collected each visit during the entire 12 week training period and end at the 6 month visit. In general, AEs should be reported and classified by the investigator using a diagnosis. The diagnosis should be confirmed through specific signs, symptoms, and (if necessary) laboratory tests. Data to be collected will include the description of the event, onset and resolution dates (or whether the event is ongoing), severity, management/treatment, outcome, and determination of the relationship to the device used during training. The relationship of the event to the device used will be further described as related or unrelated to a specific device. If related to a device, the categories will be further described as definitely, probably, or possibly-related using the following definitions:

1. *Definitely device-related:* Any event that is associated with the device by timing and physiology, and was caused or contributed to by the device.
2. *Probably device-related:* Any event that is associated with the device by timing and physiology, and there is a good chance that it may have been caused or contributed to by the device.
3. *Possibly device-related:* Any event that is associated with the device by timing and physiology, and there is a possibility that it may have been caused or contributed to by the device.

Severity of the AE will be coded as to the degree of severity as follows:

- A. *Mild:* Awareness of the event but easily tolerated.

- B. *Moderate*: Discomfort enough to cause interference with usual activity.
- C. *Severe*: Inability to carry out usual activity (not necessarily the same as a Serious Adverse Event. Subjects may have a severe flu but not require hospitalization.)

Treatment for the AE includes all of the commercially approved products or standard procedures that are to be administered according to standard medical practice. Investigational products or procedures are not to be used as a treatment for an adverse event. All unresolved AEs should be followed by the Investigator until all events are resolved, the event is identified as being a chronic condition, or the participant is lost to follow-up.

The case report form package for this study includes dedicated adverse event and serious adverse event forms.

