## **23.      Potential Risks to Study Participants and Mitigation of Risks**

- 1) The risk of falling: Having experienced therapists conduct the training sessions will minimize the risk of falling.
- 2) Risk of exceeding range of motion: This would be caused if any device moves the Participant beyond the normal range of motion, resulting in a strain, sprain or fracture. For the Ekso device, this risk is lessened by mechanical hard stops that prevent the device from exceeding a normal human range of motion even in the event of an electrical or software failure. Software systems are also in place to further reduce range of motion to improve fit and comfort during walking. Participants will be evaluated by clinicians who will eliminate Participants from being included in the study if Participants cannot meet the required range of motion. For all other devices, this risk will be mitigated through proper settings by the physical therapist in charge of Participants treatment.
- 3) Discomfort, skin pressure/friction, bruising, pain, or unusual swelling caused by any device that contacts the skin. This risk will be minimized by a thorough skin check performed by experienced personnel at each training session. Adjustments to the harness placement and additional padding will be assessed to decrease the risk of skin breakdown as well.
- 4) Blood pressure instability related to standing or activity. This risk will be reduced by checking blood pressure and heart rate prior to training, and as necessary during training and after.
- 5) Reflex bowel or bladder activity or autonomic instability during walking. This risk will be minimized by requiring Participants to relieve bowels and bladder prior to walking.
- 6) Spasms triggered by joint movement in the device. This risk will be reduced through screening prior to enrollment in the study. Participants cannot take part if the Participant's muscles are too stiff.
- 7) Any device used during this study could malfunction. In the event of device malfunction, Participants will be able to safely transfer out of the device.
- 8) There is a risk of fractures when participating in a therapy program: this will be minimized by requiring medical clearance if Participants are at risk for severe osteoporosis.

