Intent-to-treat population:	Subjects who met the inclusion criteria and were randomized to an intervention arm. Thus, enrolled in the study.
All enrolled population:	Subjects who were enrolled in the study (randomized to an intervention arm) and completed at least one day of the intervention. This group of subjects will be used for safety analysis.
Per protocol population:	All subjects who were enrolled, completed one of the three intervention arms, and were followed out to last follow-up visit after following intervention.

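### The SAP's only safety population requires randomisation, so run-in Ekso users are left out, and no rule assigns adverse events by treatment received

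*SAP*

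**What the plan says.** SAP section 1.1 lists three populations. The one called all enrolled consists of "Subjects who were enrolled in the study (randomized to an intervention arm) and completed at least one day of the intervention", and the SAP adds: "This group of subjects will be used for safety analysis". No other safety population is defined in either document.

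Protocol section 5 says: "Run-in Participants follow the same assignment as described in Group 1 but are NOT randomized". Section 8.2 gives run-ins the full 36 Ekso sessions and the Group 1 assessments, apart from the week 24 visit. The session column of Table 2 names Groups 1 and 2 and the run-in group.

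Group 3 (passive control) may choose Ekso or standard gait training after week 12. Footnote 3 to Table 2 says of that period: "The optional 12 week period will consist of training only. No further evaluations will be completed at this time". On adverse events, protocol section 12 says: "AEs will continue to be collected each visit during the entire 12 week training period and end at the 6 month visit". Table 2 gives the week 24 visit to Groups 1 and 2 only.

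Protocol section 17.1 analyses participants by randomised arm whatever they actually received. It makes no exception for safety.

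**The concern.** A device safety analysis should cover everyone who used the device in the trial and should place each event under the training in use when it occurred. This plan does not secure either.

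Run-ins are the first trial users at each site, and their adverse events and skin checks are collected, yet the safety population leaves them out. Passive controls who later train in Ekso are in the population but under the wrong heading for that period.

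At stake are the precision and completeness of the device safety summary, and any safety comparison of Ekso with passive control.

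**Working it through.** **The plan's group sizes (SAP 1.8, protocol 17.4).** The documents give no figure for the safety set, so I first checked the sizes on which the count depends.

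- Superiority over passive control, two-sided 0.05, 80% power, 2:1, SDs 0.18 and 0.108, difference 0.11: n(passive) = (0.18²/2 + 0.108²) × (1.960 + 0.842)² / 0.11² = 18.07, so 19 passive and 38 Ekso. Power at 38/19 by Welch t is 80.5%.
- Non-inferiority to active control, one-sided 0.05, margin 0.055, true difference 0.110 − 0.078 = 0.032: n = (0.18² + 0.108²) × (1.645 + 0.842)² / 0.087² = 35.99 per group. Welch t needs 37 (80.2%).

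The stated 38/38/19 reproduces.

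**Run-ins outside the safety set.** The Study Outline caps enrolment at 40 run-ins and 127 randomised 2:2:1. That gives 127 × 2/5 = 50.8 Ekso, 50.8 active and 127/5 = 25.4 passive. The lower run-in scenario is an assumption: one run-in at each of 15 sites. The lower randomised scenario is the evaluable target of 95.

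| Randomised | Run-ins | Ekso in safety set | Ekso-trained | Left out |
|---|---|---|---|---|
| 127 | 40 | 51 | 91 | 40/91 = 44% |
| 127 | 15 | 51 | 66 | 15/66 = 23% |
| 95 | 40 | 38 | 78 | 40/78 = 51% |
| 95 | 15 | 38 | 53 | 15/53 = 28% |

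**What this does to precision.** With zero events among n people, the one-sided 95% upper bound on the risk is 1 − 0.05^(1/n):

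- n = 51: 5.7%
- n = 66: 4.4%
- n = 91: 3.2%

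Pooling in this way assumes that run-in and randomised users share the same risk, so the two should also be shown apart.

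**Who is enrolled, and who is randomised.**

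- Protocol 8.1 makes a person enrolled on signing consent, and protocol 17.1 analyses all enrolled subjects. Run-ins would be included.
- The SAP's all enrolled population adds randomisation as a condition. Run-ins would be excluded.
- Protocol 5 and 8.2 say run-ins are not randomised. The SAP 1.1 description of the design reads as if those who qualify during the run-in are randomised 2:2:1.

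Two programmers working from these texts could build different safety sets.

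**Crossover events.** Up to about 25 passive participants could train in Ekso; uptake is not stated and may be anywhere from 0 to 100%. Under protocol 17.1 their events stay in the passive arm. SAP 1.1 plans tests of association between treatment group and adverse event occurrence, so an Ekso-passive comparison of that kind would be affected.

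On collection, the texts point in different directions:

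- Without a group limit: the per-session list in protocol 11 (adverse events and skin integrity), footnote 6 to Table 2 (skin before and after each training session), and the adverse event and serious adverse event rules in protocol 12.
- Against: the Table 2 session column does not name crossovers, footnote 3 allows training only, and protocol 12 closes collection at a 6-month visit that Table 2 does not give Group 3.

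**The case against.** The strongest reply is that much of the safety system does cover these people. Run-ins are expressly in the session schedule, so their data are collected. For crossovers, the per-session items and the adverse event rules carry no group limit, and protocol section 23 says of skin problems: "This risk will be minimized by a thorough skin check performed by experienced personnel at each training session". Footnote 3 excludes evaluations, a word that Table 2 uses for the midpoint, endpoint and follow-up visits and not for session assessments. Rule 7 of protocol section 10 counts sessions as visits, so a crossover's last study visit can be read as the last training session. Section 6 keeps randomised participants enrolled for about six months, which is roughly 12 passive weeks plus 12 crossover weeks. Each event is also recorded with its relationship to the device used. All of this stands. It narrows the crossover problem to inconsistent wording plus a missing attribution rule.

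It is also right that pooling non-randomised run-ins into a randomised comparison would weaken that comparison. That argues for separate display, not for omission from the device safety summary.

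Some stronger readings are tempting but not supported:

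- **That up to 25 × 36 = 900 crossover sessions have no scheduled safety items.** The unrestricted per-session list and footnote 6 contradict this.
- **That the stated safety test is biased towards the device.** The safety hypothesis in SAP 1.3 compares Ekso with active control. Crossover events booked to passive control do not enter it.
- **That crossover training breaches the 30-day rule.** The text is "Baseline examinations may not occur more than 30 days prior to initiation of the training regimen". It governs baseline examinations. Physician clearance, range of motion and arm strength sit in the screening column, which carries no such limit for any group.
- **That the safety set holds less than half of Ekso users.** At 127 randomised this needs all 40 run-ins and at least 12 of about 25 passive participants choosing Ekso: 51/(91 + 12) = 49.5%. With no crossovers it holds 51 of 91 (56%).

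**Conclusion.** The point holds for the safety set and for attribution. As written, the SAP's only safety population excludes run-in participants who train in Ekso for 36 sessions: 44% of Ekso-trained people at the caps, and 23% with 127 randomised and an assumed 15 run-ins. At the caps, including them lowers the zero-event upper bound from 5.7% to 3.2%. These shares take everyone allocated to Ekso as having trained and leave crossovers out of the count.

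The conflict over who is enrolled and randomised makes the safety set ambiguous. The lack of a treatment-received rule would put Ekso events after crossover under passive control; the size of that effect depends on an uptake that the documents do not give. Collection of adverse events during crossover training is inconsistent, and nothing here shows that it would not happen. The Ekso-active safety test is unaffected by the crossover issue. The change should be made, but the randomised comparison does not depend on it.

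**What to change.** In SAP section 1.1:

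- Define the safety set as every run-in or randomised participant with at least one day of the assigned intervention or observation period, grouped by treatment received. This keeps the SAP's existing one-day exposure condition and gives passive controls a clear entry rule.
- Show run-in and randomised Ekso users separately and pooled. Keep the formal Ekso-active comparison to randomised participants.
- Tabulate events after the first crossover session under the training then received, and end passive-arm safety time at that session.

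Across the documents:

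- Reconcile the meaning of enrolled and randomised between protocol 5, 8.1, 8.2 and 17.1 and SAP 1.1, including the SAP sentence on randomisation during the run-in.
- Reconcile Table 2, its footnote 3 and the two end points for adverse event collection in protocol 12, so that the existing per-session safety items and the adverse event window clearly cover crossover training.

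The cost is SAP wording, a short protocol clarification, one more safety table, and slightly more data entry for up to about 25 people on an existing form. No efficacy visits are added.

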## 1.2 Working Study Hypotheses

Participants undergoing exoskeleton training for 12 weeks /36 sessions will demonstrate equal progress in walking speed as those participants undergoing standard gait training for 12 weeks/36 sessions. Participants in both the exoskeleton group and the standard gait training group will show greater progress after 12 weeks/36 sessions than the participants in the passive control group.

### 1.3 Primary Endpoint

*Efficacy:* The primary endpoint is the mean increase in gait speed demonstrated during the 10MWT after 12 weeks/36 sessions of training compared to baseline and compared between groups. Both self-selected and fast speeds will be performed on the 10MWT, with the fast speed taking precedent.

Hypothesis #1: The mean change in the Ekso G intervention group will be statistically superior to that in the passive control group, as follows:

$$H_0: \mu_E \leq \mu_p \text{ vs } H_a: \mu_E > \mu_p$$

where  $\mu_E$  and  $\mu_p$  are the mean change in the Ekso G intervention group and the passive control group, respectively.

Hypothesis #2: Using the two one-sided (TOST) procedure, the null hypothesis of non-equivalence or non-inferiority of means will be tested for the Ekso GT ( $\mu_E$ ) versus the Active Control ( $\mu_A$ ) using a two-group design with equal sample sizes in the two groups. We want to demonstrate that the mean gait speeds will have similar distributions on the average for the two intervention groups. We specify that the practical difference in means is therefore defined to be 0.055 m/s, which is one-half of the hypothesized treatment effect of Ekso G over passive control as stated below, and one-eighth of the threshold of 0.44 m/s (1.0 mph) commonly used to represent gait speed associated with community ambulation. The two null hypotheses are specified below:

$$H_{01}: \mu_E - \mu_A \leq \delta_L \text{ or } H_{01}: \mu_E - \mu_A + \delta_U \leq 0 \text{ vs } H_{02}: \mu_E - \mu_A \geq \delta_L \text{ or } H_{02}: \mu_E - \mu_A - \delta_U \geq 0$$

The composite null hypothesis is that the two groups have unequal mean gait speeds. The alternative hypothesis is that the mean gait speeds are equivalent for both the Ekso G Intervention group and the active control group.

Reject  $H_{01}$  if the observed difference in the two means is too large. That is, reject if the lower bound for two-sided  $100(1-2\alpha)\%$  confidence interval for  $\mu_E - \mu_A$  is greater than the group mean multiplied by the assumed practical difference of 0.055 m/s.

Reject  $H_{02}$  if the observed difference in means is too small. That is, reject if the upper bound for the two-sided  $100(1-2\alpha)\%$  confidence interval for  $\mu_E - \mu_A$  is less than the group mean multiplied by the assumed practical difference of 0.055 m/s.

The one-sided alpha levels are fixed at 0.05 for each of the two one-sided tests and desire a power of 80% when the two gait speeds are the same true mean gait speed.

*Safety:* The occurrence of adverse events, if any, will be recorded, thoroughly investigated, documented and included in the study safety analysis. A determination will be made regarding the relationship of the adverse event to the intervention.

*Null Hypothesis:* The difference in the proportion of active control group subjects who experience a device-related adverse event and the proportion of subjects in the Ekso G intervention group to have experienced a device-related adverse event will be zero.

$$H_0: p = p_0 \text{ vs } H_a: p \neq p_0$$

